9.3. WITHDRAWAL CRITERIA

If, during the clinical investigation, a subject must be prematurely withdrawn, the procedures outlined in this section must be followed. These procedures should not interfere with the initiation of any new treatments that are necessary to treat a subject's condition. Information on all withdrawn subjects will be documented.

Subjects may be withdrawn from the clinical investigation for any of the following reasons:

- a. Subject Withdrawal: A subject may voluntarily withdraw from the clinical investigation at any time and for any reason. The subject should be asked when possible, and without any form of coercion, the reason for his/her decision. If the participant withdraws from the clinical investigation completely, then data collected up until the point of withdrawal will be included in the final analysis. Subjects who decline to continue to take part will be given the opportunity to discuss/inform the research team of the reasoning behind their decision not to take part.
- b. Lost to Follow-Up (LTFU): A subject will be considered LTFU after all reasonable efforts have been made to contact the subject and request his/her continued participation in the clinical investigation. All attempts to contact the subject must be documented and should include at least two attempts to contact the subject by phone and one attempt via a certified letter. Data collected up until the point where the subject is LTFU will be included in the final analysis.
- c. Removal of Device or Adverse Event/Incident: The discontinuation of a subject's participation in the clinical investigation due to the removal of the Tibial Nail of the T2 Alpha Tibia Nailing System or Adverse Event/incident that prohibits his/her continued participation must be fully explained. All available information concerning the removal of the device or Adverse

Event/incident should be provided. Data collected up until the point of removal or Adverse Event/incident will be included in the final analysis.

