- d. Death: The discontinuation of a subject's participation in the clinical investigation due to death must be fully explained. All available information concerning the death should be provided. Removal of a subject from continued follow-up in the clinical investigation due to death will not be considered a device failure unless the death is directly caused by, or attributable to, the T2 Tibia Nailing System. Data collected up until the point of death will be included in the final analysis.
- e. Other: A subject may be withdrawn by the Investigator if he/she believes that it is in the best interest of the subject or the IRB/EC may determine that a subject's continued participation in the clinical investigation represents an unacceptable risk to the subject. The Sponsor must be notified immediately if this occurs. All data collected up until the point of withdrawal or IRB/EC determination will be included in the final analysis.

A subject may also be withdrawn if the subject is non-compliant with the clinical investigation procedures or visits, or if a selection criteria violation is noted after the subject received the clinical investigation treatment and it is determined that the subject should be discontinued. All data collected up until the point of withdrawal will be included in the final analysis.

10. Clinical Investigation Evaluations, Procedures and Assessments

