11.3.4. Additional Analyses

Additional Analyses are outlined in the subsequent sections. Analysis details (variables, level of measurement, planned steps) are listed in-depth in the SAP.

Weight-bearing status

The weight bearing status will be evaluated and analyzed at the pre-operative visit and at 3 months, 6 months and 12 months. The within subject changes from visit to visit will be analyzed in addition. This analysis will be part of the annual and final reports.

External Support

The status of the subject using external support will be evaluated at the pre-operative visit and at 3 months, 6 months and 12 months. The within subject changes from visit to visit will be analyzed in addition. This analysis will be part of the annual and final reports.

Mortality

For analysis of the time to death or mortality, the Kaplan-Meier method will be used. The times between the date of surgery and the date of the 12 months assessment will be used together with the times between surgery and the date of death. This analysis will be part of the annual and final reports.

Reoperation

For analysis of the time to the reoperation, the Kaplan-Meier method will be used. The times between the date of surgery and the date of the 12 months assessment will be used together with the times between date of surgery and the date of reoperation (earliest reoperation in case that one subject experienced more than one reoperation). This analysis will be part of the annual and final reports.

SF-36 Total Score – Within subject changes by visit

The within subject score changes of the SF-36 Total Score from visit to visit will be analyzed to help identify the changes on the subject level. This analysis will be part of the annual and final reports.

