13.4. ADVERSE DEVICE EFFECT/INCIDENT REPORTING AND ANALYSIS

In the event that a SADE, UADE or serious incident occurs, the Investigator is required to notify the Sponsor within 48 hours of being made aware of the event. The Investigator is also required to notify their IRB/EC in accordance with the policies of their local laws and regulations.

14. Reoperations

Reoperations and reason(s) for reoperations will be collected throughout the course of the clinical investigation. A reoperation may include, but not limited to, irrigation and debridement, revision surgery, and/or implant removal.

15. Ethics

This clinical investigation is to be conducted according to International Conference of Harmonisation of Good Clinical Practice (ICH-GCP), applicable regulations, institutional research policies and procedures, Declaration of Helsinki and in compliance with the Clinical Investigation Plan (CIP). Investigators will be trained on the clinical investigation devices and surgical techniques prior to implanting clinical investigation subjects.

This CIP and any amendments will be submitted to a properly constituted independent ethics board, in agreement with local legal prescriptions, for formal approval of the clinical investigation conduct. The decision of the ethics board concerning the conduct of the clinical investigation will be made in writing to the Site Principal Investigator before commencement of this clinical investigation. Clinical investigations shall not begin until the governing regulatory authority has provided full, unconditional approval. Off-label use of the T2 Alpha Tibia Nailing System is not permitted.

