3.1.3. Additional Analyses

Additional Analyses are outlined in the subsequent sections. Analysis details (variables, level of measurement, planned steps) are listed in-depth in the SAP.

• Weight-bearing status

The weight bearing status will be evaluated and analyzed at the pre-operative visit and at 3 months, 6 months and 12 months. The within subject changes from visit to visit will be analyzed in addition. This analysis will be part of the final report.

External Support

The status of the subject using external support will be evaluated at the pre-operative visit and at 3 months, 6 months and 12 months. The within subject changes from visit to visit will be analyzed in addition. This analysis will be part of the final report.

o Mortality

For analysis of the time to death or mortality, the Kaplan-Meier method will be used. The times between the date of surgery and the date of the 12 months assessment will be used together with the times between date of surgery and the date of death. This analysis will be part of the final report.

• **Reoperation**

For analysis of the time to the reoperation, the Kaplan-Meier method will be used. The times between the date of surgery and the date of the 12 months assessment will be used together with the times between date of surgery and the date of reoperation (earliest reoperation in case that one subject experienced more than one reoperation). This analysis will be part of the final report.

• SF-36 Total Physical Score – Within subject changes by visit

The within subject score changes of the SF-36 Total Score from visit to visit will be analyzed to help identify the changes on the subject level. This analysis will be part of the final report.

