Creation of variable Difference between Date of Surgery [dd.mm.yyyy] and Date of 12 Months Visit [dd.mm.yyyy] in [days] (Variable(s): VISITDT; VISNAME)	Quantitative, ratio	N/A (Analyzed above), used for survivorship		Х	
Create new variable "Grouping variable – First Device Related Adverse Event" (Variable(s): AEEVENT)	Qualitative, nominal	- censored = survivors - events = first (earliest) Device Related Adverse Event		Х	
Create new variable "Combined Time – First Device Related Adverse Event" (Variable(s): AEONSTDT)	Quantitative, ratio	 Use time between surgery and 12 months visit for surviving subjects Use time between surgery and first device related adverse event for subjects with device related adverse event 		Х	
Use variables "Combined Time – First Device Related Adverse Event"	Qualitative,	Case summary with number and percentage of valid		Х	

and "Grouping variable – First Device Related Adverse Event"	nominal Quantitative, ratio	cases/values, missing cases/values (if any) and total cases/values. Kaplan-Meier survival analysis: subject ID, time, status, cumulative proportion, Kaplan-Meier estimate, standard error of KM estimate, number of cumulative events, number of remaining cases, mean for survival time with 95% confidence interval, survival graph bazard graph	
		survival graph, hazard graph.	

Table 6.6.3: Endpoints – Secondary Endpoint Time to (earliest) Device Related Adverse Event / Incident Tables List

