6.7.5. Revision Surgery

For analysis of the time to the revision surgery, the Kaplan-Meier method will be used. The times between surgery and the 12 months assessment will be used together with the times between surgery and the date of revision (earliest revision in case that one subject experienced more than one revision). This analysis is part of the final report.

Evaluation Variable / Question	Level of Measurement Recode and Analysis Plan				
Adverse Events / Revision Surgery					
Creation of variable Difference between Date of Surgery [dd.mm.yyyy] and Date of First Revision [dd.mm.yyyy] in [days]] (Variable(s): VISITDT)	Quantitative, ratio	Case summary with number and percentage of valid cases/values, missing cases/values (if any) and total cases/values. Mean, median, interquartile range, maximum, minimum, standard deviation, 95% confidence interval for mean, Shapiro-Wilk Test.			
Creation of variable Difference between Date of Surgery [dd.mm.yyyy] and Date of 12 Months Visit [dd.mm.yyyy] in [days] J (Variable(s): VISITDT)	Quantitative, ratio	N/A (Analyzed above), used for survivorship			
Create new variable "Grouping variable – First Revision" (Variable(s): VISITDT)	Qualitative, nominal	 - censored = survivors - events = first (earliest) Revision 			
Create new variable "Combined Time – First Revision" (Variable(s): VISITDT)	Quantitative, ratio	 Use time between surgery and 12 months visit for surviving subjects Use time between surgery and first revision for subjects with revision(s) 			
Use variables "Combined Time – First Revision" and "Grouping variable – First Revision"	Qualitative, nominal Quantitative, ratio	Case summary with number and percentage of valid cases/values, missing cases/values (if any) and total cases/values. Kaplan-Meier survival analysis: subject ID, time, status, cumulative proportion, Kaplan-Meier estimate, standard error of KM estimate, number of cumulative events, number of remaining cases, mean for survival time with 95% confidence interval, survival graph, hazard graph.			

Table 6.7.5: All Assessments – Revision Surgery Tables List

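### SAP Kaplan-Meier tables give no time to event-free subjects who leave before the 12-month visit, and SAP 6.7.5 analyses first revision where first reoperation is planned

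*SAP*

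**What the plan says.** SAP Tables 6.6.3, 6.7.4 and 6.7.5 share one construction. Status is either an event or "censored = survivors". Time runs from surgery to the event for subjects who have one. For everyone else the instruction is "Use time between surgery and 12 months visit for surviving subjects". None of the three tables names a withdrawal or last-contact date, and a date of death appears only in the mortality table. SAP 4.6 (Missing Data) asks for missing values to be counted and gives no censoring rule.

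Protocol 9.3 (Withdrawal Criteria) describes what happens to leavers' data. For loss to follow-up: "Data collected up until the point where the subject is LTFU will be included in the final analysis". For death: "Data collected up until the point of death will be included in the final analysis". It says the same of withdrawal and of device removal or an adverse event that ends participation. However, protocol 11.3.4 and SAP 3.1.3 describe the mortality and reoperation times with the same 12-month-assessment wording as the SAP tables.

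On the event, SAP 3.1.3 states "For analysis of the time to the reoperation, the Kaplan-Meier method will be used", and protocol 11.3.4 takes the "earliest reoperation in case that one subject experienced more than one reoperation". SAP 6.7.5 instead takes the "earliest revision in case that one subject experienced more than one revision". Protocol section 14 gives the scope of reoperation: "A reoperation may include, but not limited to, irrigation and debridement, revision surgery, and/or implant removal".

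**The concern.** Kaplan-Meier is used mainly because some subjects are followed for less than the full period. With event-free follow-up defined only through the 12-month visit, that use is lost: nobody is censored before the visit, and the curve at month 12 is in effect a simple proportion among a selected group. The selection is one-sided. Leavers whose event came first count in the numerator and the denominator. Leavers without an event count in neither.

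The second issue is independent of the first. If *revision* in SAP 6.7.5 means less than reoperation, the reported curve is not the one planned in the protocol and in SAP 3.1.3. The two issues can also combine. Protocol 9.3(c) foresees subjects leaving because the nail was removed. Under a narrow reading of revision, such a subject has neither an event nor a 12-month time in Table 6.7.5, and so disappears from a curve meant to show reoperations.

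At stake is the accuracy of three descriptive safety curves. Table 6.6.3 is captioned as a secondary endpoint; the other two are additional analyses. None has a test or an acceptance criterion.

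**Working it through.** **Step 1. What the tables assign.**

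| Subject | Time under the tables |
|---|---|
| Has the event, then stays or leaves | Surgery to event |
| Event-free, attends the 12-month visit | Surgery to that visit (censored) |
| Event-free, withdrawn or lost earlier | None defined |
| Dies without the event (adverse-event and revision curves) | None defined |

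**Step 2. Inputs.** The documents give no expected figure for these curves, so there is none to reproduce. From the plan: 80 subjects (SAP 2.2) and 20% drop-out, which SAP 3.2 calls worst-case, so 80 × 0.20 = 16 subjects may have no 12-month visit. Assumed: true 12-month rates p of 5, 10 and 20%; a milder drop-out of 10%; events and leaving independent and evenly spread over the year.

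**Step 3. Formula.** Let d be the drop-out rate and f the share of leavers' events that fall before they leave (0.5 if evenly spread). Per subject enrolled:

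- recorded events: p(1 − d + df)
- event-free with a 12-month visit: (1 − d)(1 − p)
- estimate as written: p(1 − d + df) / [p(1 − d + df) + (1 − d)(1 − p)]

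**Step 4. Results.** For d = 0.2, 1 − d + df = 0.9:

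- p = 5%: 0.045 / (0.045 + 0.760) = 5.6%
- p = 10%: 0.090 / (0.090 + 0.720) = 11.1%
- p = 20%: 0.180 / (0.180 + 0.640) = 22.0%

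For d = 0.1, 1 − d + df = 0.95:

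- p = 5%: 0.0475 / (0.0475 + 0.855) = 5.3%
- p = 10%: 0.095 / (0.095 + 0.810) = 10.5%
- p = 20%: 0.190 / (0.190 + 0.720) = 20.9%

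The error is therefore about 0.6 / 1.1 / 2.0 points at 20% drop-out and 0.3 / 0.5 / 0.9 at 10%.

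**Step 5. Sensitivity to when subjects leave** (d = 0.2, p = 10%). If all leave at the start (f = 0), the estimate is 0.08 / (0.08 + 0.72) = 10.0%. If all leave just before month 12 (f = 1), it is 0.10 / (0.10 + 0.72) = 12.2%.

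**Step 6. Simulation check.** In 4,000 simulated trials of 80 with even 20% drop-out, the rule as written gave 5.5 / 11.1 / 21.9%. Censoring at leaving gave 4.9 / 10.0 / 20.0%, with a sampling SD of 2.6 / 3.5 / 4.7 points. A differently built check fixed 16 event-free leavers and 8 events among 80: dropping the leavers gives 8/64 = 12.5%, against 11.2% when they are censored at exit.

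**Step 7. An influence in the other direction.** Protocol 10.3 allows the initial assessment up to 3 months after surgery, while time runs from surgery. Late joiners must be alive to consent. For mortality, if a share s joins evenly over months 0 to 3 (mean entry 1.5 months, 1.5/12 = 0.125 of the year), the estimate becomes p(1 − 0.125s) / (1 − 0.125sp). A true 5% then reads 4.9 / 4.7 / 4.4% for s = 25 / 50 / 100% (shares assumed, drop-out ignored). For adverse events, protocol 10.3 lists what is collected retrospectively after late consent (medical history, surgical procedure, SF-36), and adverse events are not on that list. Earlier events may be missed by an amount that cannot be computed.

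**Step 8. Event definition.** Protocol 11.3.4 and SAP 3.1.3 say first reoperation. SAP 6.7.5 says first revision and does not define it. Protocol 14 lists revision surgery as one kind of reoperation beside irrigation and debridement and implant removal. Table 6.7.5 names only VISITDT, whereas Table 6.6.3 names AEONSTDT and Table 6.7.4 names DOSEDD.

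**The case against.** The best answer for the plan is that nothing in the SAP orders early leavers to be excluded. SAP 5.3 refers to the protocol for withdrawal procedures, and a competent analyst would censor at last contact. A reader might infer that the SAP departs from the protocol. The documents do not support that: the omission is in both, since protocol 11.3.4 uses the same wording for mortality and reoperation and does not carry its own section 9.3 into the analysis. What remains is that no passage tells the analyst which date to use.

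A reader might also infer that leavers would be credited with a full 12 months, biasing the curves downward. The survivor time is a difference between two recorded dates, one of them the 12-month visit. Leavers have no such date, and no passage provides for supplying one.

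It may be said that *revision* is only loose wording for reoperation. It could be, and Table 6.2 counts every reoperation type. The understatement is therefore conditional on a narrow reading. Nor can one say that the event date has no source: Table 6.3.1 uses VISITDT with VISNAME for the date of surgery, so VISITDT may hold the reoperation date as well. What can be said is that the record is not identified.

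The error is also small, and protocol 10.5 (note b) asks sites to collect data outside visit windows, which should hold drop-out below the worst case. This is correct and limits the weight of the point. The secondary safety endpoint in protocol 8.2 is incidence, and Table 6.1 reports the event frequencies without these times.

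**Conclusion.** The point holds as a defect in the written rules for three descriptive curves. Followed as written, the tables drop event-free early leavers and keep leavers with an earlier event. Taken alone, that inflates the 12-month estimate by about 0.6 to 2.0 points at 20% drop-out and 0.3 to 0.9 at 10%, for true rates of 5 to 20%. These figures rest on assumed event rates and on events and drop-out being independent and evenly spread. They are below the sampling SD of about 2.6 to 4.7 points.

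It would go too far to call any of the reported curves biased upward overall: late consent may lower the mortality and adverse-event estimates, and a narrow reading of revision would lower the reoperation curve. It would also go too far to say that censoring at leaving removes all bias. That holds only if leaving is unrelated to event risk, and protocol 9.3(c) makes device removal or an adverse event a reason for leaving.

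The mismatch between revision and reoperation is a plain inconsistency, within the SAP and against the protocol. Its numerical effect cannot be computed from the documents. The primary endpoint, the sample size and the crude counts in Tables 6.1 and 6.2 are not affected.

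**What to change.** In Tables 6.6.3, 6.7.4 and 6.7.5, censor event-free subjects at the 12-month visit if attended. Otherwise censor at the last documented date on which event status is known: last contact, withdrawal or, in the adverse-event and reoperation curves, death. State that this assumes leaving is unrelated to event risk. Use the same wording in SAP 3.1.3 and, at the next amendment, in protocol 11.3.4.

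In SAP 6.7.5, make first reoperation (protocol section 14) the event, optionally show revision as a sub-category, and name the record and variable that hold the reoperation date.

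The cost is a few lines of SAP text and some programming. The sponsor needs to confirm which EDC fields hold the last-contact, withdrawal and reoperation dates. If those dates exist, no visits, subjects or data collection are added. If only attended-visit dates exist, the last one can serve while events reported after it are kept. In the simulation a true 10% then read about 10.4%, and that limit should be stated.

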8.2. SECONDARY ENDPOINTS

- Safety: Incidence of device-related adverse events by 12 months will be monitored through collection and analyses.
- Efficacy/Performance: Bone consolidation will be assessed by 12 months as measured by Investigator assessment.

9. Selection of Clinical Investigation Population

Subjects participating in this clinical investigation will be recruited from the investigator's standard subject population, where all subjects presenting for treatment of tibial fractures will be evaluated for clinical investigation participation based on the eligibility criteria listed below.

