3.1. FRAMEWORK

All quantitative variables, including those based on calculations (secondary elements), will be analyzed with a case summary evaluation before the detailed characteristics and parameter can be evaluated. A case summary contains a listing of the number of valid cases/values, missing cases/values (if any) and total cases/values in the specific analysis. In general, as central position parameter for quantitative

variables the mean and median will be analyzed. As variation parameter the standard deviation, 95% confidence interval of the mean, interquartile range and maximum and minimum will be calculated. All quantitative variables will be assessed for normality used the Shapiro-Wilk test. For optional visualization of quantitative variables, box-and-whisker plots will be used. Additional analyses like skewness and kurtosis measures of standard errors are also optional.

All qualitative variables, including those based on summaries (secondary elements), will be analyzed listing the proportions, frequencies, column and row totals and missing proportion (if any).

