6.1. HARMS AND SAFETY

Categorization and definitions of (Serious-, Unanticipated-) Adverse Device Effects, (Serious-) Incidents are given in the CIP.

Evaluation Variable / Question	Level of Measurement	Analysis Plan	Iı	nclusio	on
Adverse Events / Incidents	incusur ement		IR	FR	N/A
Device-Related Adverse Event / Incident (Variable(s): AEEVENT; AEOTHER)	Qualitative, nominal	Proportions, frequencies, column and row totals, missing proportion (if any). Listing of other Events/Incidents.	х	х	
Describe the AE/Incident (Variable(s): AEDESCRP)	Qualitative, nominal	Listing of other Events/Incidents Description.			Х
Unanticipated Adverse Device Event? (Variable(s): AEUADE)	Qualitative, nominal	Proportions, frequencies, column and row totals, missing proportion (if any).	Х	Х	
Severity (Variable(s): AESEVER)	Qualitative, nominal	Proportions, frequencies, column and row totals, missing proportion (if any).	Х	Х	
Describe Treatment: (Variable(s): ACTTREAT)	Qualitative, nominal	Listing of Treatment Description.			X
Action Taken (Variable(s): ACTNONE; ACTMEDS; ACTSURG; ACTLABOT; ACTSHORT; ACTPROHS; ACTOTHER: ACTOTHSP)	Qualitative, nominal	Proportions, frequencies, column and row totals, missing proportion (if any). Listing of given Other specifications.			X
AE Resolution (Variable(s): AERESOLV)	Qualitative, nominal	Proportions, frequencies, column and row totals, missing proportion (if any).			Х
Outcome (Variable(s): AEONWOTR; AEONWTTR; AEREWOTR; AEREWTTR; AETEDISB; AEPERMD; AESUEXP)	Qualitative, nominal	Proportions, frequencies, column and row totals, missing proportion (if any).			х
Creation of variable Number of Adverse Device Effects by Site (Variable(s): AEEVENT; SITENUM)	Qualitative, nominal	Proportions, frequencies, column and row totals, missing proportion (if any).	Х	Х	
Creation of variable Number of Adverse Device Effects per Subject and Site (Variable(s): AEEVENT; SITENUM; SUBID)	Qualitative, nominal	Proportions, frequencies, column and row totals, missing proportion (if any).	Х	Х	
Creation of variable Number of Adverse Device Effects by Visit (Variable(s): AEEVENT: VISNAME)	Qualitative, nominal	Proportions, frequencies, column and row totals, missing proportion (if any).		Х	

Table 6.1: Adverse Events / Incidents Tables List

Evaluation Variable / Question	Level of Measurement	Analysis Plan Inclusion		on	
Reoperation			IR	FR	N/A

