6.6. ANALYSIS OF CI ENDPOINTS

Evaluation Variable / Question	Level of Measurement	Analysis Plan
Endpoints – Primary Endpoint		

Use variable SF-36 Total Physical Score 12 Months [points]:

Based on the underlying distribution of the data and the result of the normality assessment, either the parametric onesample t-test or the non-parametric one-sample sign test will be used to compare the 12 months post-operative SF-36 score results of the T2 Alpha Tibia group against the value of 39.25 points.

The complete available SPSS tables content related to either the one-sample t-test or the one-sample sign test will be included in the final report (under no circumstances, creation of this analysis in any interim/annual report). (Variable(s): VISITDT; PCSSCORE)

Evaluation Variable / Question	Level of Measurement	Recode and Analysis Plan	Ir	nclusio	n
All Assessments – Fracture Healing		IR	FR	N/A	
3 Months - 4. Has the bone consolidated (consider weight- bearing, pain and imaging)? (Variable(s): VISITDT; BONECONS)	Qualitative, nominal	Proportions, frequencies, column and row totals, missing proportion (if any).		X	
6 Months - 4. Has the bone consolidated (consider weight- bearing, pain and imaging)? (Variable(s): VISITDT; BONECONS)	Qualitative, nominal Proportions, frequencies, column and row totals, missing proportion (if any).			X	
12 Months - 4. Has the bone consolidated (consider weight- bearing, pain and imaging)? (Variable(s): VISITDT; BONECONS)	Qualitative, nominal	Proportions, frequencies, column and row totals, missing proportion (if any).		Х	

Table 6.6.1: Endpoints - Primary Endpoint Tables List

Table 6.6.2: Endpoints - Secondary Endpoint Fracture Healing Tables List

Evaluation Variable / Ouestion	Level of Measurement	Recode and Analysis Plan	Iı	nclusio	on
Adverse Events – Time to (earliest) Device Related Adverse Event / Incident			IR	FR	N/A
Creation of variable Difference between Date of Surgery [dd.mm.yyyy] and Date of First Device Related Adverse Event [dd.mm.yyyy] in [days] (Variable(s): VISITDT; VISNAME; AEONSTDT)	Quantitative, ratio	Case summary with number and percentage of valid cases/values, missing cases/values (if any) and total cases/values. Mean, median, interquartile range, maximum, minimum, standard deviation, 95% confidence interval for mean, Shapiro-Wilk Test.		х	

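### Neither 12-month secondary proportion has a planned confidence interval; the intervals in SAP Table 6.6.3 are for mean times

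*SAP*

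**What the plan says.** Protocol 8.2 names two secondary endpoints: "Incidence of device-related adverse events by 12 months will be monitored through collection and analyses" and "Efficacy/Performance: Bone consolidation will be assessed by 12 months as measured by Investigator assessment". I read the first as the proportion of subjects with at least one device-related event.

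The SAP treats them as follows.

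- **General rule (SAP 3.1).** Quantitative variables get a 95% confidence interval of the mean. Qualitative variables "will be analyzed listing the proportions, frequencies, column and row totals and missing proportion (if any"), with no interval. Table 4.7 likewise sets an interval level for a mean only.
- **Consolidation (Table 6.6.2).** At 3, 6 and 12 months separately: "Proportions, frequencies, column and row totals, missing proportion (if any").
- **Device-related events (Table 6.1).** "Proportions, frequencies, column and row totals, missing proportion (if any). Listing of other Events/Incidents".
- **Time to first device-related event (Table 6.6.3).** The first row summarises days from surgery to first event, including "95% confidence interval for mean, Shapiro-Wilk Test". The Kaplan-Meier row lists the Kaplan-Meier estimate and its standard error, and then the "mean for survival time with 95% confidence interval". Subjects without an event are given the time from surgery to the 12-month visit.
- **Mortality and revision (Tables 6.7.4 and 6.7.5).** The same two kinds of interval.

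The 12-month visit has a window of plus or minus 4 weeks, and data from later visits are still to be collected (Protocol 10.5; SAP 4.4).

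**The concern.** Intervals are planned, but for quantities other than the two endpoints. Mean days to first event uses only subjects who had an event, so it carries no information on how many had none. The Kaplan-Meier mean is the area under the curve. When the longest observed time is censored, as it will be if most subjects reach 12 months without an event, that area stops at the longest observed time. The result is a restricted mean whose upper limit is set by whichever subject was seen last.

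At stake is what the final report can say. Without limits on the two proportions it would not state which event rate or which non-consolidation rate the data exclude. A printed mean of, say, 356 days with a narrow interval could be misread as the typical time to a device-related event. It is only what a 12-month incidence of about 5% produces when follow-up ends at day 365.

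**Working it through.** **Inputs.** 80 subjects enrolled and 20% drop-out (SAP 3.2) give 80 × 0.80 = 64 evaluable. The 12-month window (SAP 4.4) is 365 ± 28, so days 337 to 393. The documents give no expected event rate, so I assume 0, 3, 6 or 13 events in 64 (0, 4.7, 9.4, 20.3%).

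**The plan's own figure.** None exists for either secondary endpoint. The one planning figure, for the primary test, reproduces: noncentrality (43.48 − 39.25)/13.04 × √61 = 2.53, giving a one-sided 5% t-test power of 0.8051 against the stated 0.805.

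**Step 1: intervals for the proportions.** Exact (Clopper-Pearson) limits are beta quantiles. With no events the upper limit is 1 − 0.025^(1/n), which is 5.6% for n = 64 and 4.5% for n = 80.

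| Result | Estimate | Exact 95% CI |
|---|---|---|
| 0/64 events | 0% | 0 to 5.6% |
| 3/64 events | 4.7% | 1.0 to 13.1% |
| 6/64 events | 9.4% | 3.5 to 19.3% |
| 13/64 events | 20.3% | 11.3 to 32.2% |
| 51/64 consolidated | 79.7% | 67.8 to 88.7% |
| 58/64 consolidated | 90.6% | 80.7 to 96.5% |
| 61/64 consolidated | 95.3% | 86.9 to 99.0% |

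**Step 2: the Kaplan-Meier mean.** Suppose all x events precede the first censored visit. The curve then stays at S = 1 − x/n until the last observed day τ, and the mean is S·τ + (1 − S)·m, where m is the mean event time. With events spread evenly over days 0 to 337, m = 168.5. For x = 6 and τ = 393: 0.90625 × 393 + 0.09375 × 168.5 = 372.0.

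| Events in 64 | S | τ = 365 | τ = 393 | τ = 450 |
|---|---|---|---|---|
| 0 | 1.000 | 365.0 | 393.0 | 450.0 |
| 3 | 0.953 | 355.8 | 382.5 | 436.8 |
| 6 | 0.906 | 346.6 | 372.0 | 423.6 |
| 13 | 0.797 | 325.1 | 347.4 | 392.8 |

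Simulation with individually scattered visits (500 datasets per cell) agreed to within a day. With no events the variance sum is empty, the standard error is 0, and the interval is the single value τ.

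**Step 3: visit date against event rate.** Moving τ from 365 to 393 shifts the mean by 28·S:

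- 28.0 days at 0 events;
- 26.7 days at 3 events;
- 25.4 days at 6 events;
- 22.3 days at 13 events.

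At τ = 393, going from 0 to 6 events moves it 393.0 − 372.0 = 21.0 days, and from 0 to 13 events 393.0 − 347.4 = 45.6 days. The last visit date therefore matters more up to about 10% incidence, but not at 20%.

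**Step 4: event timing.** With six events all on day 10, 180 or 330 and every visit on day 365, the mean is 331.7, 347.7 or 361.7 days. Incidence is 9.4% each time.

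**Step 5: the quantity that answers the endpoint.** For 6/64, S = 0.906 with standard error √(0.90625 × 0.09375/64) = 0.036, wherever the last visit falls. The log-log limits are S^exp(±1.96 × 0.0364/(S·|ln S|)) = S^exp(±0.800). They give an incidence of 4.3 to 19.7%, close to the exact 3.5 to 19.3%.

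**The case against.** The secondary endpoints are descriptive. The plan sets no secondary hypothesis, threshold or performance goal. The Protocol synopsis says safety is shown through reporting of device-related events, and 8.2 says incidence is monitored. Omitting an interval therefore contradicts nothing in the plan. Moreover, Table 6.6.3 lists the Kaplan-Meier estimate with its standard error, and the frequency tables give numerators and totals, so a reader could derive an interval.

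Most of this stands, and it rules out four stronger readings.

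- A reader might infer that the Kaplan-Meier mean carries the only interval planned. It does not: the first row of Table 6.6.3 has one too, as do the matching rows of Tables 6.7.4 and 6.7.5.
- A reader might infer that the planned output can never show which rates are excluded. When events occur, limits can be derived from what is listed. With no events the standard error is zero and cannot be used, although the counts still allow an exact limit.
- A reader might infer that the visit date always outweighs the event rate. Step 3 shows that this fails at about 20% incidence.
- A reader might infer that time to first event is no endpoint at all. The SAP labels Table 6.6.3 a secondary endpoint and Protocol 11.3.3 plans the analysis; only the list in 8.2 speaks of incidence.

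What does not stand is leaving the limits to the reader. No method, denominator or time point is fixed in advance, and the interval that is printed in the survival tables is for a different quantity.

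**Conclusion.** The point holds as a reporting gap in the secondary endpoints. Neither 12-month proportion has a planned interval, and the intervals in Table 6.6.3 are for mean times that do not estimate incidence. The gap is clearest with no events: the Kaplan-Meier interval collapses to one day, while an incidence of up to 5.6% (n = 64) or 4.5% (n = 80) remains compatible with the data. With 6/64 events the Kaplan-Meier mean runs from about 347 to 424 days as the last visit moves from day 365 to day 450, at an unchanged incidence of 9.4%.

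These sizes rest on assumed event counts, 64 evaluable subjects, and events spread evenly before day 337. The absence of an interval and the zero-width result do not depend on the assumed rates. The documents do not support the inference that the trial fails its safety objective. The primary test is unaffected.

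**What to change.** 1. In Tables 6.6.3, 6.7.4 and 6.7.5, replace the Kaplan-Meier mean and its interval by the Kaplan-Meier cumulative incidence at day 365 with a log-log 95% CI. If there are no events, use the exact binomial interval and state its denominator.
2. In the same tables, censor subjects without the event who leave early at last contact. At present only the 12-month visit time is given for event-free subjects, so those who leave early have no stated time.
3. Name the day-365 incidence of first device-related event, with its interval, as the basis for the safety statement, so that two intervals for the same events do not compete.
4. In Table 6.6.2, add the proportion consolidated at any visit up to 12 months, with an exact 95% CI and a stated denominator. Count subjects whose assessment stopped after earlier consolidation as consolidated. Footnote d of the visit schedule lets assessment stop once consolidation is seen, so the 12-month row alone may omit them and would not estimate consolidation by 12 months.

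The cost is SAP wording and a few lines of output from data already collected. No additional subjects or visits are needed.
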